## 4.4 Multiplicity Strategy

No multiplicity adjustment needs to be considered for the effectiveness endpoints since no formal hypothesis testing will be conducted.

## 4.5 Subgroup Analyses and Effect of Baseline Factors

It is not expected that demographic or baseline characteristics will have an impact on the study results in this study. No subgroup analyses are planned.

## 4.6 Interim Analysis for Effectiveness

No interim analysis is planned for effectiveness endpoints.

## **5 Safety Analysis Strategy**

### **5.1 Safety Endpoints**

The safety endpoints are

- Adverse events (AE)
- Biomicroscopy findings
  - Limbal hyperemia
  - Bulbar hyperemia
  - Corneal staining
  - Conjunctival staining
  - Palpebral conjunctival observations
  - Corneal epithelial edema
  - Corneal stromal edema
  - Corneal vascularization
  - Conjunctival compression/indentation
  - Chemosis
  - Corneal infiltrates
  - Other findings
- Device deficiencies

### **5.2 Safety Hypotheses**

There are no formal safety hypotheses in this study. The focus of the safety analysis will be a comprehensive descriptive assessment of safety endpoints listed in Section 5.1.

### **5.3 Statistical Methods for Safety Analyses**

The analysis set for all safety analyses is defined in Section 2.1. Baseline will be defined as the last measurement prior to exposure to study lenses (ie, Visit 1). Safety variables will be summarized descriptively.

#### **5.3.1 Adverse Events**

The applicable definition of an AE is in the study protocol. All AEs occurring from when a subject signs informed consent to when a subject exits the study will be accounted for in the reporting.

Pre-treatment AEs will be separated from treatment-emergent AEs occurring during the study period. A pre-treatment AE is an event that occurs after signing informed consent but prior to exposure to study lenses. The period for treatment-emergent AE analysis starts from exposure to study lenses until the subject completes or is discontinued from the study. Each AE will be summarized under the exposed lens based upon the event onset date/time, up until the start of the next lens in the crossover sequence.

The following tables and supportive listings will be provided:

- Incidence of All Ocular Treatment-Emergent Adverse Events
- Incidence of All Nonocular Treatment-Emergent Adverse Events
- Listing of All Ocular Treatment-Emergent Adverse Events
- Listing of All Nonocular Treatment-Emergent Adverse Events
- Listing of All Ocular Pre-Treatment Adverse Events
- Listing of All Nonocular Pre-Treatment Adverse Events

### **5.3.2 Biomicroscopy Findings**

The following tables and supportive listings will be provided:

- Frequency and Percentage for Biomicroscopy Findings by Visit
- Incidence of Increased Severity by 2 or More Grades in Biomicroscopy Findings
- Listing of Subjects With Other Biomicroscopy Findings
- Listing of Subjects With Increased Severity by 1 Grade in Biomicroscopy Findings [This listing will include all relevant visits within the crossover period]
- Listing of Subjects With Increased Severity by 2 or More Grades in Biomicroscopy Findings [This listing will include all relevant visits within the crossover period]
- Listings of Subjects with Infiltrates

### **5.3.3 Device Deficiencies**

The following tables and supportive listings will be provided:

- Frequency of Treatment-Emergent Device Deficiencies
- Listing of Treatment-Emergent Device Deficiencies
- Listing of Device Deficiencies Prior To Treatment Exposure

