10.	Based upon the randomized treatment sequence, have the subject insert the appropriate Lens 1 study lenses, being careful to maintain the correct OD and OS lens assignments. [REDACTED] 
 
• Keep all lidding foils of lenses used during lens fit process for study lens accountability.
 
• Follow procedures to maintain masking.
 

11.	
Evaluate the study lenses by performing the following:
 

• logMAR VA with study lenses (OD and OS, at distance)*

 
*VA w/study lenses must be 20/25 in each eye or better for subject to leave the office

13.	
Assess and record any AEs and device deficiencies reported or observed during the study visit.
 
Note: AEs and device deficiencies must be recorded for all enrolled subjects from the time of signature of informed consent including those that screen fail.

14.	
Dispense study lenses, new lens case, and lens care solution.
 
Provide the subject with written and verbal instructions on lens wear and care.

16.	
Schedule Visit 2 to take place on study Lens 1 Day <math>8 \pm 2</math> days.
 
Note: Schedule Visit 2 at a time of day that allows a minimum of 6 hours of lens wear prior to visit.
 
Remind the subject of the following:
 

• To not use any lubricating drops during lens wear

• To wear the lenses at least 5 days a week and 8 hours per day

• To wear study lenses a minimum of 6 hours on the day of their follow-up study visit

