### 6.2 Analysis Data Sets

#### 6.2.1 Safety Analysis Set

Safety analyses will be conducted using the safety analysis set on a treatment-emergent basis. As such, the safety analysis set will include all subjects/eyes exposed to any study lenses evaluated in this study. For treatment-emergent safety analyses, subjects/eyes will be categorized under the actual study lenses exposed.

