## 6.8 Safety Analysis

The safety endpoints for this study are AEs, biomicroscopy findings, and device deficiencies.

Descriptive summaries (counts and percentages) for ocular and nonocular AEs will be presented by Medical Dictionary for Regulatory Activities Preferred Terms. AEs leading to study discontinuation, significant non-serious AEs, and SAEs will be identified. Individual subject listings will be provided, as necessary.

Individual subject listings will be provided for AEs that occur after signing informed consent but prior to exposure to study lenses.

Each biomicroscopy parameter will be tabulated by its grade. For each biomicroscopy parameter, counts and percentages of eyes that experience an increase of  $\geq 2$  grades from baseline (Visit 1) to any subsequent visit will be presented. A supportive listing will be generated which will include all biomicroscopy data from all visits in the corresponding period for these eyes experiencing the increase.

Two listings (prior to exposure of study lenses and treatment-emergent) of device deficiencies, as recorded on the Device Deficiency Form, will be provided. Additionally, each device deficiency category will be tabulated.

No inferential testing will be done for safety analysis.

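### Does restricting the SAP's device-deficiency table to treatment-emergent deficiencies leave lens defects found before wear uncounted?

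*SAP*

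**What the plan says.** SAP 5.3.3 names three outputs for device deficiencies. The only table is "Frequency of Treatment-Emergent Device Deficiencies". The others are a listing of treatment-emergent deficiencies and a "Listing of Device Deficiencies Prior To Treatment Exposure".

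Protocol 6.8 plans "Two listings (prior to exposure of study lenses and treatment-emergent) of device deficiencies", based on the Device Deficiency Form, and then adds: "Additionally, each device deficiency category will be tabulated". That last sentence carries no timing limit of its own. Protocol 6.2.1 does set one for safety work in general: "Safety analyses will be conducted using the safety analysis set on a treatment-emergent basis". SAP 2.1 repeats it and places subjects and eyes under the lens they were actually exposed to.

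The rules on timing and on assignment to a lens are written for adverse events only, in SAP 5.3.1: "The period for treatment-emergent AE analysis starts from exposure to study lenses", and "Each AE will be summarized under the exposed lens based upon the event onset date/time". SAP 5.3.3 has no counterpart.

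Collection starts before any lens is worn. Protocol 5.1.1 states that "AEs and device deficiencies must be recorded for all enrolled subjects from the time of signature of informed consent". The examples under Device Deficiencies in Protocol 7.1 include lenses torn in the pack or while being handled, and packaging faults.

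**The concern.** A deficiency belongs to a product, whereas an adverse event happens to a person. A torn lens, a leaking blister or a wrong label can be found before anything touches the eye, so a filter based on exposure looks like the wrong tool for counting such faults. Three worries follow.

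- **Scope.** Protocol 6.8 can be read as asking for a table of all deficiencies, which the SAP then narrows.
- **Definition.** If treatment-emergent means after wearing the particular lens concerned, every fault found before insertion drops out of the table, at Visit 3 as well as Visit 1.
- **Ownership.** If the adverse-event rule were borrowed, a fault in a test lens opened at Visit 3 could be dated to the Biofinity period and counted there.

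Device deficiencies are one of three safety endpoints, and Protocol 3.1 says the data are meant to inform lens development. Incomplete or misassigned counts by product would weaken that use.

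**Working it through.** There is no stated figure to reproduce and no test to check. The documents give no defect rate, so the number of affected events cannot be estimated. The check is a comparison of texts and a count of lens openings.

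**1. Scope of the table.** Protocol 6.8 names device deficiencies as a safety endpoint. Protocol 6.2.1 places safety analyses on a treatment-emergent basis. Read together, the tabulation sentence in 6.8 inherits that basis, and SAP 5.3.3 follows it. Adverse events are treated the same way in SAP 5.3.1: incidence tables for treatment-emergent events, listings for earlier ones. The tabulation sentence is ambiguous on its own, but nothing in the protocol contradicts the SAP.

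**2. Meaning of the term.** Two readings are possible.

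| Reading | Support in the documents | Defects listed only |
|---|---|---|
| A: after first exposure to any study lens | Protocol 6.8 splits the listings at exposure to study lenses; Protocol 6.2.1 and SAP 2.1 admit subjects exposed to any of them; SAP 5.3.1 starts its period at the same point | Those found before first insertion at Visit 1 |
| B: after exposure to the particular lens | No passage restarts exposure for each lens when defining the term | All those found before insertion |

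Reading A is the natural one. Under it, faults in Lens 2 packs at Visit 3 enter the table, as do faults in replacement lenses fetched during wear (Protocol 4.1).

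**3. Share of openings affected.** Inputs: about 36 enrolled and 32 to complete (SAP Table 1-1), bilateral wear, two periods, 1:1 sequences (Protocol 4). Assume one lens per eye per period, no replacements, no screen failures and an exact 18/18 split.

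- Scheduled openings: 36 × 2 eyes × 2 periods = 144. With 32 subjects: 128.
- Openings at Visit 1: 36 × 2 = 72. With 32 subjects: 64.
- Share before first exposure under reading A: 72/144 = 64/128 = 50%.
- By product at Visit 1: 18 × 2 = 36 test and 36 Biofinity lenses.

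These are illustrative counts and not upper bounds. The visit procedures allow more than one lens to be opened while fitting, and replacements add more. In the other direction, the fellow lens may be opened after the first is already on the eye. Under reading B the share would be 144/144.

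**4. Ownership.** The onset-date rule in SAP 5.3.1 is confined to adverse events, and nothing extends it to deficiencies. If it were extended, up to 18 × 2 = 36 test lenses opened at Visit 3 in Sequence 2, and 36 Biofinity lenses in Sequence 1, would be open to misassignment, on the same assumptions as step 3. But Protocol 6.8 reports deficiencies from the Device Deficiency Form, and Protocol 4.2 sends deficient study lenses back to the sponsor for investigation. The faulty product should therefore be identifiable without using dates. Lens care solution raises no ownership question, because Protocol 7.3 routes its deficiencies to spontaneous reporting.

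**5. What is lost.** The two listings together cover every deficiency, before and after exposure. With about 36 subjects, the pre-exposure listing can be counted by hand.

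**The case for a change.** The best argument for a change is that a deficiency has nothing to do with exposure, that the protocol deliberately collects faults from consent onward, and that complete counts by category and product are what lens development needs. The cost would be a sentence or two in the SAP and a different table filter. The general rule in SAP 2.1 does not fill the gap either: it classifies subjects and eyes by the lens worn, and a lens discarded before insertion was worn by nobody.

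Part of this stands. The term is undefined for deficiencies, and ownership of a fault in an unworn lens is not stated. A definition would do no harm.

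The rest does not carry far enough. The exposure filter is the protocol's own basis for safety analyses, so a wider table would depart from it. It could also bring in deficiencies recorded for enrolled subjects who were never exposed, who lie outside the Safety Analysis Set, and so raise a denominator question that the present table avoids. The misassignment route requires an analyst to apply an adverse-event date rule to a product fault when the product itself is known, which is an unlikely choice and not one the plan makes. Moving the pre-exposure counts from a listing into a table is a matter of presentation.

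**Conclusion.** No change follows. The plan as written reports every recorded study-lens deficiency either in a correctly labelled table or in a listing. The restriction agrees with Protocol 6.2.1 and mirrors the handling of adverse events. On the natural reading, the part listed without being tabulated is limited to faults found before first insertion at Visit 1, about half of scheduled lens openings, and with 1:1 sequences it falls about equally on the two products.

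No conclusion depends on it. Safety is summarized without inferential testing (Protocol 6.8), and the SAP's Executive Summary says success criteria do not apply. The missing definition and ownership rule are gaps an analyst would fill sensibly: exposure to any study lens as the dividing point, and the product recorded as deficient as the owner.

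This rests on two assumptions. The first is that treatment-emergent is read as it is elsewhere in both documents. The second is that the Device Deficiency Form, which is not among the documents, or the returned lens identifies the product. If the product could not be identified, the ownership point would matter more, but a change of table filter would not cure it.

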## 6 Analysis Strategy for Other Endpoints

Not Applicable.

## 7 Sample Size and Power Calculations

[Redacted]

## 8 References

Not Applicable.

## 9 Revision History

This is the first revision (Version 2.0) of the Statistical Analysis Plan for this study. This version of the Statistical Analysis Plan is based on Version 2.0 of the study protocol.

[Redacted]

[Redacted]

[Redacted]	[Redacted]
[Redacted]	[Redacted]
[Redacted]	[Redacted] t.

10 Appendix  
 Table 10-2 Overview of Study Plan

Procedure/ Assessment	Visit 1 Screen / Baseline/ Lens 1: Dispense [Day 1]	Visit 2 Lens 1: Week 1 Follow-up [Day 8 (± 2 days)] §	Visit 3 Lens 1: Month 1 Follow-up [Day 30 (± 2 days)] Lens 2: Dispense [Day 1]		Visit 4 Lens 2: Week 1 Follow-up [Day 8 (± 2 days)] §	Visit 5 Lens 2: Month 1 Follow-up/ Exit^ [Day 30 (± 2 days)] §	Unscheduled Visit
			Follow-up Lens 1 §	Dispense Lens 2			
Informed Consent	X						
Demographics	X						
Medical History	X	X	X	X	X	X	X
Concomitant Medications	X	X	X	X	X	X	X
Inclusion/ Exclusion	X						
Habitual lens (brand, power*, care)	X						
VA w/ habitual correction* (OD, OS, logMAR distance)	X					X	(X)
████████████████████	█		█			█	
Manifest refraction*	X	(X)	(X)	(X)	(X)	(X)	(X)
BCVA* (OD, OS, logMAR distance with manifest refraction)	X	(X)	(X)	(X)	(X)	(X)	(X)
Biomicroscopy	X	X	X		X	X	X
████████████████████	█	█	█	█	█	█	█
Randomization	X						
Dispense study lenses	X			X			(X)
VA w/ study lenses, (OD, OS, logMAR distance)	X	X	X	X	X	X	(X)
████████████████████	█	█	█	█	█	█	█

Printed By:

Print Date:

Procedure/ Assessment	Visit 1 Screen / Baseline/ Lens 1: Dispense [Day 1]	Visit 2 Lens 1: Week 1 Follow-up [Day 8 (± 2 days)] §	Visit 3 Lens 1: Month 1 Follow-up [Day 30 (± 2 days)] Lens 2: Dispense [Day 1]		Visit 4 Lens 2: Week 1 Follow-up [Day 8 (± 2 days)] §	Visit 5 Lens 2: Month 1 Follow-up/ Exit^ [Day 30 (± 2 days)] §	Unscheduled Visit
			Follow-up Lens 1 §	Dispense Lens 2			
[REDACTED]	█	█	█	█	█	█	█
[REDACTED]	█	█	█	█	█	█	█
[REDACTED]	█	█	█	█	█	█	█
[REDACTED]		█			█		█
[REDACTED]							
[REDACTED]							
[REDACTED]							
[REDACTED]							
AEs	X	X	X	X	X	X	X
Device deficiencies	X	X	X	X	X	X	X
Exit Form	(X)	(X)	(X)	(X)	(X)	X	(X)

\* Source only

§ Subjects are required to wear the study lenses for a minimum of 6 hours on the day of follow-up visits prior to the visit.

[REDACTED]
